Each patient participant will be randomized to one of two groups. Participants in the control group will receive noise-cancelling wireless headphones that will not play any noise throughout the procedure. Participants in the experimental group will receive the same noise-cancelling wireless headphones but will be permitted to listen to the music of their choice while in the operating room. Music will be provided via Spotify, which is an Internet streaming music service, and will be played through headphones; this way, no other individual in the operating room will be distracted or influenced by the patient's music selection. Participants will not be able to change the Spotify channel. We will be using the paid Spotify service with no commercials. If participants opt to have the music stopped, we will withdraw them from the study and continue standard of care. The participants will have the music playing for about two hours. If the participant has no music preference, the music will be chosen for them and it will be the same for all participants that have no preference. The volume will be adjusted in the operating room until the participant approves of the volume by saying "yes, the volume is good" or giving another verbal cue of approval. The music will continue playing until the surgical procedure is complete and the patient has reached the post-anesthesia recovery unit.

As stated previously, spinal anesthesia provides numbness that negates the need for general anesthesia, but patients often times need additional sedation, which will be defined as anesthesia medication that is

used to treat patient anxiety and discomfort in the operating room. Patient participants in both groups will receive sedation via the same protocol, which is outlined below.

It is important to note that the standard of care for this procedure involves the administration of sedation that is given at the anesthesiologist's discretion; sedation is generally given when the patient exhibits signs of discomfort or anxiety. The protocol described below is designed specifically for this study in order to provide standardization within the study participants; the protocol instructions fall within the standard of care for the administration of sedation by an anesthesia provider.

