Sedation will only be given as needed per patient request; the patient will be given a noise-making device (such as a rubber duckie that makes sound when squeezed) that will inform the anesthesia provider that the patient is uncomfortable and needs some sedation. A weight based dose of 0.3 micrograms per kilogram of intravenous propofol will be given for each patient request. This dose is expected to provide amnesia or light sleep for a few minutes. For patient safety, if the patient requests sedation more than once within a two minute window, the anesthesia provider will not administer any more medication during this two minute period. Additionally, the anesthesia provider may withhold sedation if he or she determines with physical exam and hemodynamic monitors that the patient is already over-sedated.

After five propofol boluses have been given to a patient, a propofol continuous infusion will be initiated at 25mcg/kg/min. The patient may still request additional sedation with the request instrument if he or she is still conscious enough to do so. If the anesthesia provider has given more than five boluses even with the baseline propofol infusion, the infusion will be increased to 50mcg/kg/min. In the highly unlikely scenario that five additional boluses are required with a propofol infusion rate of 50 mcg/kg/min, the anesthesia providers and investigators will make a clinical decision as to what is the safest next step.

There may be scenarios that warrant conversion to general anesthesia. These scenarios include, but are not limited to, hemodynamic instability, regurgitation of gastric content, obtundation, excessive agitation, and inadequate spinal anesthesia. The decision to convert to the general anesthesia will be made by the anesthesiologist and anesthesia provider in the operating room; implementation of this study should not prevent or delay this decision if it is necessary.

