Documentation will be completed by the anesthesia provider per standard protocol for electronic anesthesia charting at VCU. This will allow for data acquisition by the investigators through the anesthesiology printed record in Cerner. The primary outcome for this study will be the amount of sedation required during the surgical procedure; this will be calculated into micrograms of propofol per kilogram per minute. For this study, propofol will be used during the surgical procedure and intravenous midazolam and intrathecal morphine will be used for the spinal procedure; no other sedating

medications will be used. The secondary outcomes for this study will include pain scores and patient satisfaction at determined time intervals before and after the surgery.

Primary data elements that will be obtained are as follows: 1) the total amount of propofol given, 2) the duration of operating room time, which will be defined as "in the operating room" time to "out of the operating room" time. Data will be entered into a spreadsheet; the amount of propofol per unit of time will be calculated by dividing #2 from #1; if there is a difference and it is statistically significant, then our hypothesis is true.

Secondary data elements will include numerical pain scores, which are taken via standard of care nursing assessment immediately after surgery and every four hours afterwards; the study will collect the numerical pain scores that describe each four hour interval for a 24 hour time period. The numerical pain scores will be collected through the patient's medical record after the 24 hour time period has passed. Data will placed into a spreadsheet and a statistical analysis will be performed for each time interval. This will answer the question of whether or not post-operative pain scores are affected the music intervention.

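### The primary outcome is declared per kilogram per minute, but the printed calculation leaves out body weight

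*Protocol*

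**What the plan says.** All the relevant text is in the Methods section of the protocol.

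- **Outcome and unit.** "The primary outcome for this study will be the amount of sedation required during the surgical procedure", and "this will be calculated into micrograms of propofol per kilogram per minute".
- **Data elements.** The next paragraph names two primary elements: "1) the total amount of propofol given, 2) the duration of operating room time". The second runs from room entry to room exit. Body weight is not listed.
- **Calculation.** "the amount of propofol per unit of time will be calculated by dividing #2 from #1".
- **Decision.** The same sentence ends: "if there is a difference and it is statistically significant, then our hypothesis is true".
- **Dosing.** Boluses and infusion both follow weight: "A weight based dose of 0.3 micrograms per kilogram of intravenous propofol will be given for each patient request", and after five boluses "a propofol continuous infusion will be initiated at 25mcg/kg/min".

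No other part of the protocol brings weight into the outcome calculation.

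**The concern.** The unit and the formula have different dimensions. The unit is mass per weight per time; the formula gives mass per time. The protocol fixes both, so this is a contradiction in its text and not a detail left for a statistical analysis plan. A plan that followed either statement would conflict with the other.

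The difference matters because every dose is scaled to weight. Total propofol therefore rises with body weight even when the need for sedation, per kilogram, is the same. Under the printed formula the sole primary outcome partly measures how heavy the participant is. Two analysts working from the same page could compute different variables and obtain different p-values, which leaves room to choose after the data are seen.

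**Working it through.** The protocol gives no figure for this outcome (no mean, SD, effect size or sample size), so there is nothing to reproduce. The check is dimensional, followed by an illustration.

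**Dimensions**

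- Declared unit: mcg / kg / min.
- Printed formula: element 1 (mcg) / element 2 (min) = mcg / min.
- The missing factor is 1/kg.

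**Inputs for the illustration**

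- From Methods, used exactly as printed and for arithmetic only: 0.3 mcg/kg per bolus, five boluses before the infusion starts, infusion at 25 mcg/kg/min.
- Assumed: 120 min in the room, borrowed from "The participants will have the music playing for about two hours", which describes the music and not room time; infusion for 60 or 40 min; body weights of 60 to 120 kg.

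**Same sedation, different weight**

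Per-kilogram total = 5 × 0.3 + 25 × 60 = 1,501.5 mcg/kg. Divided by 120 min, this is 12.51 mcg/kg/min at every weight. The printed formula multiplies that rate by weight:

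| Weight (kg) | Declared unit (mcg/kg/min) | Printed formula (mcg/min) |
|---|---|---|
| 60 | 12.51 | 750.75 |
| 80 | 12.51 | 1,001.0 |
| 100 | 12.51 | 1,251.25 |
| 120 | 12.51 | 1,501.5 |

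The ratio of scores equals the ratio of weights, whatever the per-kilogram dose or duration. The boluses supply only 1.5 of the 1,501.5 mcg/kg, so the result hardly depends on the bolus figure.

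**Reversal of order**

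With 40 min of infusion: 5 × 0.3 + 25 × 40 = 1,001.5 mcg/kg, and 1,001.5 / 120 = 8.35 mcg/kg/min. That is 8.35 / 12.51 = 0.667 of the other participant's rate, or 33% less. At 120 kg the printed formula gives 8.3458 × 120 = 1,001.5 mcg/min, against 750.75 mcg/min for the 60 kg participant with 60 min. The ratio is 1.334, or 33% more. For this pair of rates the order reverses once the weight ratio exceeds 12.5125 / 8.3458 = 1.50, that is, above about 90 kg against 60 kg.

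**Loss of precision**

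Let c be the CV of the per-kilogram rate and w the CV of weight, with the two independent. The squared CV of their product is c² + w² + c²w², so relative variance is multiplied by (c² + w² + c²w²) / c² = 1 + w²/c² + w².

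| w | c = 0.5 | c = 0.8 | c = 1.0 |
|---|---|---|---|
| 0.20 | 1.20 | 1.10 | 1.08 |
| 0.25 | 1.31 | 1.16 | 1.125 |

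In sample-size terms, assume a 30% relative difference, two-sided alpha 0.05 and 80% power. With c = 0.5, the number per arm is 44 with the weight term, and 49 to 58 without it for w from 0.15 to 0.25. With c = 1.0, it is 175 with the weight term and 183 to 197 without it. None of these inputs is in the protocol.

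**The case against.** The strongest reply is that the protocol names one primary outcome, with its unit, and that the later sentence is loose shorthand for part of the derivation. Dividing by time is a necessary step towards mcg/kg/min, and an analyst who respects the unit must also divide by weight. Weight has to be known for anyone given propofol, because dosing depends on it. On this reading the formula is incomplete, and no second outcome exists.

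That reading may well be what the investigators intend, but the document does not say so. It lists a closed pair of elements, describes the first as a total amount, and ties the verdict on the hypothesis to their ratio. Followed literally, it yields the wrong variable.

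The criticism of the magnitude has more force. The 60 and 120 kg pair is extreme, and the twofold gap simply restates that choice. The worked example applies only to participants who went past five boluses. Since sedation is given only on request, zero or very low use is plausible, and a zero stays zero at any weight. A widely spread per-kilogram rate also shrinks the penalty: at c = 1.5 the formula above gives only about 6% to 9%. If per-kilogram use falls as weight rises, the inflation could shrink further or vanish. These points limit the size of the effect; they do not remove the contradiction.

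**Conclusion.** The concern holds and should be fixed. The mismatch between unit and formula rests on the text alone and needs no assumption. Its practical effect is ambiguity about the sole primary outcome and, if the printed formula is used, extra weight-related variance: about 8% to 31% for a weight CV of 20% to 25%, a per-kilogram rate CV of 0.5 to 1.0, and independence. It is not a systematic bias, because randomisation balances weight on average, although a chance imbalance in weight between the groups would shift the comparison. The individual examples show the mechanism and do not describe the expected trial population.

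**What to change.** Add body weight, specified as the weight used for dosing, as the third primary data element. Replace the calculation sentence with: primary outcome = total propofol (mcg) / body weight (kg) / operating-room time (min). Tie the statement about the hypothesis to that variable. This keeps the sponsor's declared unit and changes no dose or procedure.

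The cost is one sentence of protocol wording and one chart field that weight-based dosing already requires, with no added visit or participants. The change should be made before outcome data are compared between the groups.
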